### **7.3 Study Validity**

For a valid study, the positive control must make the same objectives that the test formulation does and both the test formulation and the positive control should be superior to the negative control for the primary endpoint. The responder rates for both active and inactive treatments at 6 hours are near 100%. Therefore, comparison of responder rates at 6 hours is unlikely to show any difference. Differences in log10 CFU/cm^2 reductions from baseline will be used at 6 hours in order to show active treatments are more effective than the inactive control.

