#### **16.2 Efficacy (Primary) Analyses**

CFU values will be calculated as per Section 13.9. Individual plate CFU counts that are zero will be treated as 0.5 for further calculations. Changes from baseline will be calculated separately for each subject and for each of the three non-baseline sites by taking the baseline  $\log_{10}$  CFU/cm^2 values and then subtracting the  $\log_{10}$  CFU/cm^2 values for the samples taken after the baseline. Therefore, a subject who completes all treatments and passes all baseline requirements will have 4 (sites) \* 3 (post-application samples per site) = 12 changes from baseline reported. Responder status will be calculated for each reported  $\log_{10}$  CFU/cm^2 reduction. The sites will be considered responders based on the sample time and body area:

For the groin at 30 seconds or 10 minutes, a  $\log_{10}$  CFU/cm^2 reduction  $\geq 3.0$  is considered a responder.

For the abdomen at 30 seconds or 10 minutes, a  $\log_{10}$  CFU/cm^2 reduction  $\geq 2.0$  is considered a responder.

For either the groin or the abdomen at 6 hours, a  $\log_{10}$  CFU/cm^2 value less than baseline (i.e., a  $\log_{10}$  CFU/cm^2 reduction  $> 0$ ) is considered a responder.

Responder statuses will be grouped by body area, sample time, and test substance. Exact confidence intervals will be calculated for responder rates. The primary efficacy goal is to have the 95% confidence intervals for the responder rate at 10 minutes to be  $\geq 70\%$ . The secondary efficacy goals are to have the 30-second and 6-hour 95% confidence intervals for the responder rates to be  $\geq 70\%$ .

Differences in responder rates between treatments and their confidence intervals will be calculated using asymptotic (approximate) methods. If differences in responder rates are not reliable based on approximate methods, which happens when rates are near either 100% or 0%,  $\log_{10}$  CFU/cm^2 confidence intervals for the differences will be used for comparison instead.

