Two-sided confidence intervals for  $\log_{10}$  CFU/cm^2 changes from baseline will also be calculated. These calculations will use an ANOVA model with subject as a random variable and test substance as a fixed variable. Body area (abdomen or groin) will be a fixed variable. Sample times (30 seconds, 10 minutes, or 6 hours) will be calculated separately using identical models. Differences in  $\log_{10}$  CFU/cm^2 reductions will be calculated based on the same model.

Any deviation(s) from the statistical analysis plan will be described and justified in the final report.

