Average Treatment Effect (ATE) will be estimated from a linear regression of post-treatment bacterial count ( $\log_{10}$  scale) on the additive effect of a treatment indicator and the baseline or pretreatment measurement ( $\log_{10}$  scale). ATE will be calculated for the 10-minute samples separately for each product and each body area. [REDACTED]

The ATEs will be compared as follows:

- a. ZuraPrep™ will be compared to the ChloraPrep®. To show effectiveness, ZuraPrep™ should be non-inferior to ChloraPrep® with a 0.5 margin. Specifically, the upper bound of the 95% confidence interval of the ATE of ChloraPrep® minus the ATE of ZuraPrep™ should be less than or equal to 0.5.
- b. ZuraPrep™ will be compared to ZuraPrep™ vehicle. To show effectiveness, ZuraPrep™ should be superior to ZuraPrep™ vehicle by a 1.2 margin. Specifically, the lower bound of the 95% confidence interval of the ATE of ZuraPrep™ minus the ATE of ZuraPrep™ vehicle should be greater than or equal to 1.2.

The same ATE calculations will be performed for the 30-second time point, but the results are for informational purposes only.

PROTOCOL AMENDMENT FORM

DATE: 08/29/2017

PROTOCOL NUMBER: 150316-103

APPROVALS:

[REDACTED]

  
STUDY DIRECTOR / PRINCIPAL INVESTIGATOR

08/29/17

DATE

[REDACTED]

REVIEWED BY:

[REDACTED]

[REDACTED]

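### The 6-hour comparison of the actives with vehicle adjusts for test-day baseline only by subtraction, which costs precision unless the true baseline slope is near 1

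*Combined protocol and SAP*

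**What the plan says.** Section 16.2 builds the outcome by subtraction: "Changes from baseline will be calculated separately for each subject and for each of the three non-baseline sites", as baseline log10 minus the later log10 value. For intervals on these reductions, "These calculations will use an ANOVA model with subject as a random variable and test substance as a fixed variable". One more term is listed: "Body area (abdomen or groin) will be a fixed variable". The model is repeated at each time: "Sample times (30 seconds, 10 minutes, or 6 hours) will be calculated separately using identical models". Treatment differences in log10 reduction come from the same model. No baseline covariate is named.

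Section 7.3 gives this model its role at 6 hours. It states that "The responder rates for both active and inactive treatments at 6 hours are near 100" per cent, so a comparison of rates is unlikely to separate the arms. It therefore says that differences in log10 "reductions from baseline will be used at 6 hours in order to show active treatments are more effective than the inactive control".

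The amendment of 29 August 2017 adds an average treatment effect (ATE) analysis, which regresses the post-treatment log10 count "on the additive effect of a treatment indicator and the baseline or pretreatment measurement". Its visible text applies this at 10 minutes, and at 30 seconds for information. At 6 hours the amended Section 7.2 keeps responder rates and adds no ATE.

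**The concern.** Subtracting baseline is a form of adjustment, but one that presumes a one-log higher baseline goes with a one-log higher count after treatment. The design gives reasons to expect less than that at 6 hours. Baseline and 6-hour samples come from different, randomly assigned spots (Sections 13.3 and 13.5). Each baseline is one sample read on duplicate plates (Section 13.7). Zero counts are set to 0.5 (Section 13.9), which puts a floor under heavily reduced counts. These are inferences from the design; no slope is reported.

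If the slope is below 1, subtraction puts baseline noise into the outcome. Part of any chance baseline difference between the active and vehicle sites then appears as a treatment difference. What is at stake is the precision of the 6-hour active-minus-vehicle difference, which is limited by the small vehicle arm. The plan already adjusts for baseline by regression at 10 minutes, so 6 hours is the odd one out.

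**Working it through.** **Inputs from the documents.** Section 11.1 gives 288 test-product/positive-control pairs and 32 pairs of vehicle with each active. The counts reproduce: 288 + 32 + 32 = 352 subjects; 352 x 2 = 704 site evaluations per body area; 288 + 32 = 320 sites per active; 32 + 32 = 64 vehicle sites. The analysable baseline windows (Section 7.1) are 3.0-5.5 log10 for abdomen and 5.0-7.5 for groin, each 2.5 wide.

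**Inputs assumed.** No SD, correlation or power basis is visible. Baseline SD is taken as 0.50 or 0.72 (2.5/sqrt(12) = 0.72, a uniform spread over the window), post-treatment SD as 0.7 or 1.0, correlation r as 0 to 0.7, and within-subject correlation as 0.5. The confidence level for these intervals is not stated; 95% is assumed.

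**Closed form.** Let k = SD post / SD baseline, so the slope of post on baseline is b = rk.

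- In units of the baseline variance, the change score has variance 1 + k² - 2rk. The residual after regression on baseline has variance k²(1 - r²).
- The difference is 1 - 2rk + r²k² = (1 - b)². With a slope common to all arms, subtraction is therefore as good as regression only when b = 1.
- The width ratio, adjusted to change score, is sqrt[k²(1 - r²)/(1 + k² - 2rk)]. With k = 1 and r = 0.3 this is sqrt(0.91/1.40) = 0.81. At r = 0, 0.5, 0.7 and 0.9 it is 0.71, 0.87, 0.92 and 0.98.

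**Simulation of the paired design.** One body area, 288/32/32 pairs, random subject, REML, 300 runs per setting, test product minus vehicle. Selected settings of 16:

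| Baseline SD | Post SD | r | Width, change score | Width, baseline added | Ratio |
|---|---|---|---|---|---|
| 0.72 | 0.7 | 0 | 0.450 | 0.314 | 0.70 |
| 0.72 | 0.7 | 0.3 | 0.376 | 0.299 | 0.79 |
| 0.72 | 0.7 | 0.5 | 0.319 | 0.272 | 0.85 |
| 0.72 | 0.7 | 0.7 | 0.247 | 0.225 | 0.91 |
| 0.72 | 1.0 | 0.3 | 0.466 | 0.427 | 0.92 |
| 0.50 | 1.0 | 0.5 | 0.388 | 0.389 | 1.00 |

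Across all 16 the ratio runs from 0.70 to 1.00 and is about 1.00 only where the slope is about 1. The closed form gives larger gains if post-treatment counts vary less than baseline (0.60 at k = 0.75, r = 0), but that case was not simulated.

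**Chance imbalance.** With baseline SD 0.6 and sites treated as independent, the SE of the baseline difference is 0.6 x sqrt(1/320 + 1/64) = 0.082 log10. With pairing and within-subject correlation 0.5 it is about 0.07. The part that reaches the treatment difference is (1 - b) times this: at b = 0.3, 0.7 x 0.07 = 0.05 log10.

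**Slopes that differ by arm.** The results above assume one slope in every arm. With baseline and residual SD 0.6 and within-subject correlation 0.5, the SE ratio of a common-slope covariate model to the change score is:

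| Slope, active | Slope, vehicle | SE ratio |
|---|---|---|
| 0.1 | 0.1 | 0.74 |
| 0.1 | 0.6 | 0.94 |
| 0.1 | 0.7 | 1.02 |
| 0.1 | 0.8 | 1.06 |
| 0.1 | 0.9 | 1.13 |
| 0.3 | 0.9 | 1.07 |

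With 320 against 64 sites, the active arm dominates a common slope, which then fits vehicle badly. With centred baseline and a separate slope per test substance, the ratio was 0.75 to 0.94 in every setting examined.

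**The case against.** The strongest objection is that covariate adjustment is not automatically better here. Vehicle lacks the alcohol, so its counts may follow baseline more closely than those of the actives, and under this allocation a common-slope model can then widen the interval. That stands, and it determines the form of the fix.

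Several stronger readings are tempting, and the documents do not support them.

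- A reader might infer that baseline is ignored. It is not; it is subtracted.
- A reader might infer that imbalance passes in full into the result. Only (1 - slope) of it does.
- A reader might infer bias or a false-positive problem. Assignment is randomised, and the simulated rejection rate under no difference averaged 5.9% for both models over the 16 settings, against a nominal 5%.
- A reader might infer that this is the only planned active-vehicle comparison at 6 hours. Section 16.2 also says "Differences in responder rates between treatments and their confidence intervals will be calculated using asymptotic (approximate) methods", with no limit on time point. However, Section 7.3 expects these to be uninformative at 6 hours, and Section 16.2 falls back on log10 differences when rates are near 100%.

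The stakes are also limited. Section 7.3 requires superiority over vehicle for the primary endpoint, which is at 10 minutes. The stated 6-hour goal is a responder-rate interval against 70%, which this model does not touch. The change score is valid and matches the plan's own measure. These arguments hold down the severity, but they do not explain why the 6-hour contrast lacks the adjustment used at 10 minutes.

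**Conclusion.** The point holds as one of precision in a secondary comparison. The Section 16.2 model fixes the baseline slope at 1 in the analysis that Section 7.3 relies on at 6 hours, and the ATE amendment, as far as its text is visible, does not cover that time. The comparison is unbiased on average. Where slopes are similar across arms, adjustment narrows the interval by 0 to 30% under the assumed SDs and correlations, and by nothing when the slope is 1. The carried imbalance is (1 - slope) times a quantity with SD about 0.07 log10, on the assumption of baseline SD 0.6 and within-subject correlation 0.5. The simulations treat one body area, whereas the planned model fits both together, so the absolute widths are illustrative. Nothing in the documents shows that the 6-hour conclusion is at risk. Severity is modest.

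**What to change.** In Section 16.2, add test-day baseline log10 CFU/cm² to the log10-reduction model at all three times. Centre it within body area, let its slope differ by body area and by test substance, and keep subject random. Name this model as the source of the 6-hour active-minus-vehicle differences for both actives. The slope by test substance is needed because a single common slope could widen the interval if vehicle counts track baseline much more closely than active counts.

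No new data are needed, since every analysed site must already have a qualifying test-day baseline. The cost is slightly more analysis work and a few extra parameters. The August 2017 amendment was issued after testing ended, so the change must be recorded as post-testing and justified in the final report, with the unadjusted change-score result shown beside it.

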### **13.5 Experimental Period**

Prior to sampling, the subjects will be questioned regarding adherence to the protocol. Female subjects must have a negative urine pregnancy test documented before treatment with test materials.

Subjects will don a disposable undergarment and be examined physically to ensure no evidence of injury, dermatosis, or dermatitis is present at the test sites (Section 15.2). On the abdomen, a sterile surgical marker will be used to demarcate bilaterally 5" x 5" areas of skin to the right and left side of the navel that appear to be similar in condition. On the groin, a sterile surgical marker will be used to demarcate bilaterally 1.5" x 5" areas of skin that appear to be similar in condition.

Prior to collection of the baseline, 30-second, 10-minute, and 6-hour post-prep samples, the skin in each test area will be evaluated for indications of skin irritation, based on the Skin Irritation Scoring System (Section 15.2).

Subjects will be sampled for baseline microbial population on sites randomly assigned on the skin of the abdomen and groin on both sides (Appendix 2). The Cylinder Sampling (Scrub Cup) Technique (Section 13.6) will be used for this and for the post-treatment samples.

The randomly assigned test product, positive control, and negative control will be applied to the test sites per directions presented in Appendix 1. A total of three post treatment sample collections will be performed at each test site for all test materials. All subjects will have samples collected within 30 seconds  $\pm$  5 seconds, 10 minutes  $\pm$  30 seconds and 6 hours  $\pm$  30 minutes post application from both anatomical treatment sites. Following the 10-minute sample being obtained the remaining sample sites will be covered with sterile synthetic-blend gauze sponges and semi-occlusive catheter dressings. Subjects will return 6 hours following product application to be sampled. During product applications, subjects will wear disposable gloves to guard against contamination of the test sites.

If the semi-occlusive catheter dressing has lifted from a test site such that the gauze sponge is no longer secured, the test site will be sampled and the occurrence noted.

Following completion of the final post-product application sampling of a test site, the remaining test material will be wiped/cleansed from the test site with a mild soap and/or tap water.

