**PROTOCOL AMENDMENT FORM**

**DATE:** 03/30/2017

**PROTOCOL NUMBER:** 150316-103

PROTOCOL AMENDMENT FORM

DATE: 04/06/2017

PROTOCOL NUMBER: 150316-103

SPONSOR: Zurex Pharma, Inc.

PROTOCOL TITLE: PIVOTAL CLINICAL EVALUATION OF [REDACTED] A PATIENT PREOPERATIVE SKIN PREPARATION (Sponsor Project Number: ZX-ZP-0074)

REASON(S) FOR CHANGE(S): To update and clarify the randomization section of the protocol as a result of the changes implemented in Protocol Amendment Form 03 (screening day baseline criteria expansion).

[REDACTED]  
In Section 13.3, Randomization, under "Treatment Balance", the sentence:

"Each subject will receive two different treatments, one on the right side of the body and one on the left."

Will be changed to:

"Each subject will receive two different treatments *per anatomical site* (abdomen or groin), one on the left and one on the right. A subject that has qualifying screening baselines on both anatomical sites may receive up to 3 different treatments."

[REDACTED]  
STUDY DIRECTOR / PRINCIPAL INVESTIGATOR

04/06/17

DATE

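### The log10-reduction ANOVA pools abdomen and groin with subject as its only random term, so it does not reflect the left/right pairing within body area; unless the correlations happen to be equal, its product-difference intervals are miscalibrated or inefficient.

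*Combined protocol and SAP*

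**What the plan says.** Section 16.2 sets out the model for changes from baseline in log10 counts: "These calculations will use an ANOVA model with subject as a random variable and test substance as a fixed variable". It adds: "Body area (abdomen or groin) will be a fixed variable". Only the time points are split: "Sample times (30 seconds, 10 minutes, or 6 hours) will be calculated separately using identical models". Differences between products in log10 "reductions will be calculated based on the same model". The intervals are two-sided. Their level is not restated there, so 95% is carried over from the responder-rate goals in the same section.

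A complete subject supplies four sites, hence four observations to each time-point model. Products are compared left against right. Section 13.5 has the two abdominal areas marked on "areas of skin to the right and left side of the navel that appear to be similar in condition", and the groin areas are chosen in the same way. The 04/06/2017 amendment to Section 13.3 assigns two products within each anatomical site and adds: "A subject that has qualifying screening baselines on both anatomical sites may receive up to 3 different treatments". The 03/30/2017 amendment lets a subject enter on one body area only. The 08/29/2017 amendment adds a regression for average treatment effects (ATEs), done by body area, and leaves this ANOVA as it was.

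The intervals have two uses. Section 7.3 says that differences in log10 reduction "will be used at 6 hours in order to show active treatments are more effective than the inactive control". Section 16.2 also falls back on them when responder-rate differences are unreliable because rates are near 0% or 100%.

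**The concern.** A single random subject term implies one common correlation among all four sites, so left and right abdomen are modelled as no more alike than abdomen and groin. The unit within which products are compared is the left/right pair in one body area. Variation between a subject's two areas cancels in a left/right difference, yet this model puts it in the residual that sets the width of every product difference.

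An error in the other direction is also possible. A subject who carries the same two products in both areas supplies two product differences, which the model treats as independent. If a subject's response to a product is shared across areas, they are not independent.

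At stake are the precision and calibration of the comparison meant to separate the actives from vehicle at 6 hours, and of the fallback comparison.

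**Working it through.** **Design counts.** From Sections 7.0 and 11.1: 288 + 32 + 32 = 352 subjects; 352 × 2 = 704 sites per area; 288 + 32 = 320 sites per active; 32 + 32 = 64 vehicle sites per area. These match the plan.

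**Assumptions.** The documents available give no SD or correlation for log10 reductions. Set the total variance to 1, the left/right correlation to rw and the abdomen/groin correlation to rb. The residual variance is then ve = 1 − rw and the subject-by-area variance is vsa = rw − rb.

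**Formula, ZuraPrep minus ChloraPrep, four sites per subject, same pair in both areas.** The true error of a left/right difference depends on ve alone. The listed model's residual tends to ve + (2/3)vsa. The ratio of reported to correct SE is therefore √(1 + (2/3)vsa/ve).

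- At rw = 0.5, rb = 0.1: √(1 + (2/3)(0.4)/0.5) = √1.533 = 1.24.
- The same by averaging the six pairwise correlations: (2 × 0.5 + 4 × 0.1)/6 = 0.233; √((1 − 0.233)/(1 − 0.5)) = 1.24.
- At rw = rb the ratio is 1, so nothing is lost.

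**Simulation at 0.5/0.1** (288/32/32 subjects, REML, 1,000 trials, then a repeat with 2,000):

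| Contrast | Mean reported SE | Empirical SD | Ratio | False-positive rate |
|---|---|---|---|---|
| ZuraPrep − ChloraPrep, 1,000 trials | 0.0496 | 0.0395 | 1.26 | 2.0% |
| ZuraPrep − ChloraPrep, 2,000 trials | 0.0496 | 0.0416 | 1.19 | 1.8% |
| ZuraPrep − vehicle, 1,000 trials | 0.0966 | 0.0831 | 1.16 | not recorded |
| ZuraPrep − vehicle, 2,000 trials | 0.0967 | 0.0834 | 1.16 | 2.2% |

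SEs are in units of the total SD.

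**Simulated coverage of nominal 95% intervals** for rw/rb of 0.3/0.1, 0.5/0.2, 0.5/0 and 0.7/0.2:

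| Design | ZuraPrep − ChloraPrep | ZuraPrep − vehicle |
|---|---|---|
| Same pair in both areas | 96.8% to 99.6% | 96.5% to 99.4% |
| Pairs drawn independently by area | 96.8% to 99.2% | 95.2% to 96.7% |
| Half the pairs from one-area subjects | 97.0% to 98.7% | 95.9% to 98.2% |

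In the second row the vehicle interval is nearly calibrated, but the estimate is inefficient. At 0.7/0.2 its empirical SD is 0.077, against 0.066 for a model that respects the pairing.

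**Opposite direction.** Give the same product pair to both areas and add a shared within-subject product effect as an extra cross-area correlation. The false-positive rates below are for the ChloraPrep and vehicle contrasts respectively.

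- Extra correlation 0.2: 4.6% and 4.4% (repeat: 5.8% and 4.9%). The two errors roughly cancel.
- Extra correlation 0.4: 8.5% and 8.3% (repeat: 9.4% and 8.6%).

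**Practical size for vehicle.** The difference detectable with 80% power is about 2.8 × SE. That is 2.8 × 0.0831 = 0.23 SD with correct errors and 2.8 × 0.0966 = 0.27 SD as listed. For an assumed SD of 0.5 to 1.5 log10, it moves from 0.12 to 0.14 at the low end and from 0.35 to 0.41 at the high end.

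**The case against.** The strongest reply is that little depends on this. The primary endpoint uses exact intervals for responder rates. Non-inferiority to ChloraPrep is judged by the by-area ATE regression, so the contrast most affected here carries no success criterion in the ANOVA. For the vehicle contrast that Section 7.3 relies on, coverage is near nominal once pairs differ by area. The detectable difference moves by at most about 0.06 log10 over the assumed SD range, against a superiority margin over vehicle of 1.2 log10 at 10 minutes. The only direct support for closer left/right agreement is a visual match of skin condition, which says nothing certain about changes from baseline. For one-area subjects a random subject term already is the left/right pair.

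Most of this stands, and it limits the weight of the point. It does not rescue the model: the common correlation is imposed by the stated terms, and no other section relaxes it for this ANOVA.

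A reader might infer two stronger things. One is that the intervals cannot be 95% intervals. The documents do not support that: they give no correlations, equal correlations leave the intervals intact, and opposing errors can cancel. The other is that the model invites false claims of superiority over vehicle. That needs a strong shared product effect across areas, which nothing in the documents suggests. The more likely error is conservative.

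**Conclusion.** The error structure in Section 16.2 does not match the within-area pairing. It gives correct and efficient product-difference intervals only if left/right and abdomen/groin correlations are equal and no product effect is shared across areas within a subject. If left/right sites are more alike, the intervals are usually too wide: about 24% too large an SE for ZuraPrep-ChloraPrep at assumed correlations 0.5/0.1, and less for vehicle. Under the amended pairing, what remains for vehicle is mostly lost efficiency. All sizes rest on assumed correlations and equal variances.

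The primary endpoint is unaffected, and a large 6-hour difference from vehicle would still be detected. This is a correction worth making to a supporting analysis. It does not threaten the main conclusion.

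**What to change.** In Section 16.2, fit the ANOVA separately for abdomen and groin at each sample time, with subject random and test substance fixed; report product differences by area and state the 95% level. Each subject then contributes one left/right pair, which removes both the subject-by-area problem and the double counting across areas. Simulated false-positive rates for the separate fits were 4.2% to 6.4%. It also matches how responder rates and ATEs are already handled.

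If one pooled model is kept, add a random subject-by-body-area term and use subject-clustered standard errors with a small-sample correction. The random term alone is not enough: with a shared product effect it gave 8.6% to 12.9% false positives. Uncorrected clustered errors reached 6.8%, highest for vehicle; the corrected version was not simulated.

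The cost is one sentence and no new data. The downside is two intervals, each from fewer sites. Using the 288 direct pairs alone at rw = 0.5, the ZuraPrep-ChloraPrep SE is √(2 × 0.5/288) = 0.059 SD per area, against √(2 × 0.5/576) = 0.042 pooled. Because the 08/29/2017 amendment says testing was already complete, the change should be reported and justified as a deviation, as Section 16.2 requires, with the listed model's results shown beside it.

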## PROTOCOL AMENDMENT FORM

DATE: 03/30/2017

PROTOCOL NUMBER: 150316-103

SPONSOR: Zurex Pharma, Inc.

PROTOCOL TITLE: PIVOTAL CLINICAL EVALUATION OF [REDACTED] A PATIENT PREOPERATIVE SKIN PREPARATION (Sponsor Project Number: ZX-ZP-0074)

**REASON(S) FOR CHANGE(S):** The inclusion criterion regarding baseline screening results have been expanded to allow subjects to proceed to Treatment Day if they have passing Screening Day baseline counts on the left and right sides of the abdomen and /or the left and right sides of the groin due to recruitment challenges around subjects meeting the minimum screening baseline requirements in the abdomen.

Section 11.3, Criteria for Inclusion, second bullet point (page 17) will state the following:

Have Screening Day baseline counts of at least  $1.0 \times 10^3$  CFU/cm^2 per abdominal site (left and right) and/or at least  $1.0 \times 10^5$  CFU/cm^2 per groin site (left and right).

Section 13.4, Baseline-Screening Sampling: The third paragraph will state the following:

Baseline criteria for qualification for the test period are  $3.0 \log_{10}$  CFU/cm^2 from the skin of the abdomen, and  $5.0 \log_{10}$  CFU/cm^2 on the skin on the groin. Subjects may qualify on either one or both anatomical site(s) and be admitted into testing for those anatomical site(s) only, or one if the sample size minimums have been met for an anatomical region. If more subjects qualify for treatment than can be treated in a given time period, preferential admittance into the treatment phase will be given to subjects qualifying in both the abdominal and inguinal test areas, followed by subjects who pass abdomen only. Subjects that qualify may be moved to a future group for testing the following week without having to re-qualify (clip or go through screening baseline again). If subjects that qualify need to move to a future group later than the following week, the subjects will be required to re-qualify (clip if needed and go through screening baseline). Subjects who do not qualify may be allowed to be screened again at the discretion of the Principal Investigator.

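### The log10-reduction ANOVA, as specified, yields one treatment difference for abdomen and groin combined, so the 6-hour and fallback comparisons with vehicle are not by area

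*Combined protocol and SAP*

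**What the plan says.** **The model.** Section 16.2 makes subject a random factor and test substance a fixed factor in the ANOVA of log10 change from baseline. It then states: "Body area (abdomen or groin) will be a fixed variable". What is split is time: "Sample times (30 seconds, 10 minutes, or 6 hours) will be calculated separately using identical models". Treatment differences in log10 reduction come from that same model. No test substance × body area term, by-area fit or by-area contrast is mentioned.

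**Where the model is used.**
- Section 7.3 expects 6-hour responder rates near 100% on active and inactive treatments alike. It therefore says that differences in log10 reduction "will be used at 6 hours in order to show active treatments are more effective than the inactive control".
- Section 16.2 has a fallback for comparing treatments: "If differences in responder rates are not reliable based on approximate methods, which happens when rates are near either 100% or 0"%, log10 intervals for the differences replace the responder-rate differences.

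**How the other efficacy analyses treat area.**
- For responder rates: "Responder statuses will be grouped by body area, sample time, and test substance".
- For the ATE regression, added to Section 16.2 by the amendment of 08/29/2017: "ATE will be calculated for the 10-minute samples separately for each product and each body area". It continues: "The same ATE calculations will be performed for the 30-second time point, but the results are for informational purposes only". The amendment gives no ATE at 6 hours. Its listed comparisons are ZuraPrep with ChloraPrep and ZuraPrep with vehicle, not ChloraPrep with vehicle.

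**The concern.** In a model with test substance and body area as main effects only, the area term shifts the mean level and each treatment contrast has a single coefficient. That coefficient is a valid average over the two areas, but it cannot show that an active product beats vehicle in each of them. If it is read that way, an effect confined to the groin can be reported as an effect on the abdomen as well.

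The plan gives no ground for assuming equal differences. Section 7.1 sets different treatment-day baseline ranges for the two areas (3.0–5.5 and 5.0–7.5 log10) and different 10-minute criteria (2.0 and 3.0 log10).

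Two comparisons have no by-area log10 analysis elsewhere in the plan: any active product against vehicle at 6 hours, and ChloraPrep against vehicle whenever the fallback applies. The second bears on study validity, because Section 7.3 asks that the positive control also be superior to the negative control on the primary endpoint.

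**Working it through.** **1. Design counts (Sections 7.0 and 11.1).** Pairings are 288 ZuraPrep–ChloraPrep, 32 ZuraPrep–vehicle and 32 ChloraPrep–vehicle.
- Subjects: 288 + 32 + 32 = 352.
- Sites per area: 2 × 352 = 704, which reproduces the stated figure.
- Sites per area by product: 288 + 32 = 320 for each active product and 32 + 32 = 64 for vehicle.

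The public text of Section 7.4 gives no SD or power, so none can be reproduced.

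**2. What the listed terms estimate.** Model as written: reduction = intercept + substance + area + subject (random) + error. With 704 sites in each area and the same pairings in both, the generalised least squares expectation of the active–vehicle coefficient is the equal-weight average:

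δ(pooled) = ½ δ(abdomen) + ½ δ(groin)

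True differences of 0 and 0.5 give 0.25; 0 and 1.0 give 0.50; 0.8 and 0.8 give 0.80. Adding substance × area recovers each area's own difference.

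**3. Standard errors.** Assumed, not in the documents: SD of log10 reduction 0.8–1.3, correlation between any two sites on one subject 0.3–0.5. Both areas are taken to carry the same pairings within a subject.

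| SD | Correlation | SE, pooled | SE, one area |
|---|---|---|---|
| 0.8 | 0.5 | 0.068 | 0.087 |
| 1.0 | 0.3 | 0.095 | 0.125 |
| 1.3 | 0.3 | 0.123 | 0.162 |

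**4. Chance of apparent superiority when the abdomen has no effect.** P(95% lower bound > 0) = Φ(δ/SE − 1.96). With a groin effect of 0.5, δ(pooled) = 0.25:
- SD 1.0, correlation 0.3: Φ(0.25/0.095 − 1.96) = Φ(0.67) ≈ 0.75.
- Worst precision: Φ(0.25/0.123 − 1.96) = Φ(0.07) ≈ 0.53.
- Best precision: Φ(0.25/0.068 − 1.96) = Φ(1.72) ≈ 0.96.
- Abdomen-specific contrast: Φ(0 − 1.96) = 0.025.

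Simulation with a REML random-intercept fit (2,000 replicates per setting) over the same SD and correlation range:

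| True groin effect (abdomen 0) | Mean pooled difference | Pooled lower bound > 0 |
|---|---|---|
| 0.25 | 0.12 | 17–47% |
| 0.5 | 0.25 | 52–96% |
| 1.0 | 0.50 | 98–100% |

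The abdomen-specific contrast gave 2–3%. At a groin effect of 0.5, the pooled interval contained the true abdominal value in 4–48% of trials. ChloraPrep against vehicle gave the same 52–96%.

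**5. Effect of the enrolment amendments.** Under the amendment of 03/30/2017, "Subjects may qualify on either one or both anatomical site(s) and be admitted into testing for those anatomical site(s) only". The amendment of 04/06/2017 allows up to three treatments per subject across areas. At a groin effect of 0.5 (1,000 replicates per setting), the pooled lower bound exceeded zero as follows:
- Pairings assigned independently per area: 62–99%.
- Half of each area's subjects entered for that area only: 55–97%.
- Groin sites 1.5 times abdominal sites: 81–100%, with a mean pooled difference of 0.31.

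The last case shows that the weights depend on the achieved area mix, so the pooled quantity is not fixed in advance.

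**6. When effects are equal.** With 0.5 in both areas the pooled model is unbiased and its interval coverage is 94–95%.

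**The case against.** The strongest reply is that the text is silent and does not declare pooling. Section 16.2 never says additive or averaged over areas, and an analyst could add the interaction. Responder status is grouped by area, so a log10 substitute for a by-area comparison would naturally be by area too. This stands in part: the model is under-specified. But the plan says what is fitted separately and lists only sample times, and a pivotal analysis should not leave the term to be chosen after the data are seen.

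Second, Section 7.3 names no area and sets no margin at 6 hours, and it ties the superiority condition to the primary endpoint. The formal 6-hour responder goal is already by area. This is correct and limits the weight of the point. Section 7.3 still states that the 6-hour log10 comparison is meant to show the active products work better than vehicle.

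Third, ATE covers ZuraPrep against vehicle by area at 10 minutes with a 1.2 log10 margin. The amended Section 7.2 also sets 30-second ATE goals identical to those at 10 minutes, although the amended Section 16.2 calls the 30-second results informational. This narrows the exposure at those times but leaves 6 hours and ChloraPrep against vehicle uncovered. Nothing in the plan shows that the fallback will be triggered at 10 minutes.

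Fourth, a zero abdominal effect is a chosen scenario, and the poor coverage of the abdominal value simply reflects that the pooled interval estimates something else. Both remarks are fair. The figures illustrate the size of a misreading; they do not predict one.

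**Conclusion.** The concern holds. Fitted with the terms listed, the ANOVA gives one difference per treatment pair at each time point, averaged over abdomen and groin, and so does not support a by-area statement against vehicle at 6 hours or in the fallback. With no abdominal effect and a groin effect of 0.5 log10, the pooled analysis would indicate superiority in roughly 52–96% of trials, where an abdomen-specific contrast would do so in 2–3%. These sizes rest on the assumed SD, correlation and effects. The point should be fixed, but it does not touch the 10-minute responder-rate goals or the ATE criteria, and it does no harm if the treatment differences are equal in both areas.

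**What to change.** In Section 16.2, either fit the log10-reduction model separately for abdomen and groin at each time point, or add test substance × body area and report area-specific contrasts. State that these contrasts are the ones used for the 6-hour comparison in Section 7.3 and for the responder-rate fallback, including ChloraPrep against vehicle. State the confidence level as well: the ANOVA sentence says only that the intervals are two-sided.

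Testing was complete by the amendment of 08/29/2017, so the change should be documented and justified as Section 16.2 already requires for departures from the analysis plan.

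The cost is about one sentence, a small code change and some precision. At SD 1.0 and correlation 0.3 the standard error rises from 0.095 to 0.125; over the assumed range it is 0.087–0.162 against 0.068–0.123. At a true difference of 0.5 in both areas, simulated power is 88–100% for the abdomen-specific contrast against 98–100% pooled. At the least precise setting the formula gives Φ(0.5/0.162 − 1.96) ≈ 0.87.

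Treatment-day log10 baseline could be added as a covariate to match the ATE model. This is optional and separate from the defect.
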